## **8. STUDY DESIGN**

### **8.1 STUDY DESIGN**

This is a randomized, parallel group study. Subjects will be randomly assigned in a 5:3 ratio of ALNB:SC. Subjects will be stratified by ulcer type (PU, DFU, LU).

Participation in the study will last up to 12 weeks. Subjects will be required to make at least one visit per week to the research site. The primary clinical endpoint will be six (6) weeks from enrollment, with clinical data also collected at three (3) and twelve (12) week follow-up visits. Health care resource use data will be gathered and compared over the entire twelve week study period.

**Figure 8.1-1: Overview of Study Design**

## 8.2 RATIONALE

This post-market clinical study is required for regulatory purposes and will be the first clinical evaluation of ALNB following its launch. This pilot study will gather preliminary data regarding the use of this new dressing in subjects with chronic, moderate to highly exuding ulcers in an outpatient clinical care setting. Both subject population and setting were selected due to market considerations. When compared to SC, this study will provide important evidence to support product claims, reinforce continuing regulatory approval, and provide both an estimate of effect size and test of study feasibility to guide the development of potential future full-scale RCT testing the efficacy and cost-effectiveness of ALNB.

The impact of treatment on HRQoL is a common outcome across a wide range of health interventions and medical conditions, including advanced wound care. The CWIS was chosen for use in this study due to its focus on the quality of life in subjects with chronic wounds, and supporting evidence for reliability and validity. Within this self-reported questionnaire, the

CWIS-PSDL scale was selected as the primary outcome measure due to relevance to key product claims for ALNB, including those concerning fluid handling/leakage, pain, comfort, and odor control.

In addition to evaluating the impact on quality of life, this study will also seek to estimate the effects of ALNB on ulcer progression, healthcare resource use, gather safety data, and explore dressing performance.

### **8.3 METHODS USED TO MINIMIZE BIAS**

Blinding of subjects and HCP to treatment allocation is not possible due to obvious physical differences in the appearance of dressings and sterile packaging. Bias reduction will consist of subjects randomly allocated to the two groups, ALNB and SC, to control for the influence of extraneous variables on treatment outcomes. In this way, no Investigator will be able to direct a particular subject to a particular treatment. Baseline procedures and assessments are performed prior to assigning the subject to a treatment group. SC was selected as the comparator treatment, rather than a specific competitor dressing, together with the recruitment of subjects from multiple treatment facilities to widen the generalizability of results to normal clinical practice.

Unequal allocation of subjects in favor of ALNB will ensure that twenty-five (25) subjects receive treatment with ALNB, which is viewed as a reasonable minimum requirement in providing basic safety data for the primary dressing of interest. Additionally, treatment allocation will be stratified by ulcer type to safeguard against major imbalances in clinical characteristics at baseline and aid comparability between groups.

## **9. STUDY PROCEDURE**

### **9.1 INFORMED CONSENT**

Before conducting any study procedures or examinations, the purpose and nature of the study will be explained to the subject in their native language. The subject will then read, sign, and date the Institutional Review Board (IRB)-approved informed consent document (see below for difficulties with reading and writing). Additionally, the individual who obtains consent from the

subject will sign and date the informed consent document. A photocopy of the signed informed consent document will be provided to the subject and a copy will be placed in the subject's medical record, with the original filed in the Investigator site file (ISF). Any additional requirements required by the IRB will be followed.

### **Subjects lacking mental capacity**

The minimum age for participation in the study is eighteen (18) years. Adults who lack the mental capacity to understand study information and provide informed consent without assistance from a legally appointed representative will not be permitted to take part in the study. This criterion is necessary due to demands of study participation, including completion of self-reported outcome measures.

### **Difficulties with reading or writing**

If the subject is unable to read or write, the informed consent document and associated study information will be read aloud to the subject in the presence of an independent witness. If possible, the subject shall sign and personally date the informed consent form. Where this is not possible the subject will provide verbal consent to participate in the study. The witness will then personally sign and date the informed consent form, attesting that the information was accurately explained and that the informed consent was freely given.

## **9.2 VISITS AND EXAMINATIONS**

### **9.2.1 Summary**

For a summary of the required procedures by visit, see Table 9.2-1.

**Table 9.2-1: Study Plan**

Procedure	Key Visits			Other Visits
	Visit 1 (Baseline)	Visit 2 (Day 21±3) and Visit 3 (Day 42±4)	End of Study Visit (Day 84±4)	
Informed Consent	✓			
Demographics/Medical History	✓			
Concomitant Medication	✓	✓	✓	✓
CWIS	✓	✓	✓	✓
Ulcer Assessment	✓	✓	✓	✓
ABI	✓ 			
Verify Inclusion/Exclusion	✓			
Allocate Study ID Number	✓			
Randomize	✓			
Photograph Ulcer	✓	✓	✓	✓ 
Photograph Dressing	✓ 	✓	✓	✓ 
Dressing Change		✓		✓
Complete Questions about Dressing (Subject and Investigator)	✓	✓	✓	✓
Pain scale		✓	✓	✓
Record Adverse Events (AE)	✓	✓	✓	✓
Record Device Deficiencies (DevD)	✓	✓	✓	✓
Complete Exit Form			✓	

 If not obtained within last 30 days for DFU/LU subjects

 Only if AE related to ulcer is observed

 Only if DevD observed

### 9.2.2 Visit 1 – Initial Visit (Baseline, Day 1)

1. Obtain written informed consent from the subject as detailed in section 9.1.
2. Obtain demographic information, relevant medical history, and relevant concomitant medications.
3. Screen the subject against protocol inclusion and exclusion criteria.
4. Provide the subject with a copy of the CWIS, and allow sufficient time to complete it. Staff should not assist the subject with the questionnaire, other than to instruct the subject to complete all questions. Ensure that the subject has completed the CWIS questionnaire appropriately, providing a single valid response for each item of the questionnaire.

NOTE: subjects who cannot read/write may have the CWIS read aloud to them and the subject's responses recorded. Ensure this process is noted in the source documents.
5. Complete an ulcer assessment (see Section 9.5.1) including ulcer classification, i.e. pressure ulcer staging or Wagner classification for DFU (see Section 9.5.5).
6. If the reference ulcer is a DFU or LU, determine ABI. Values obtained within the last 30 days may be used to qualify the subject.

Note for DFU subjects: Subjects with a DFU and an ABI value less than 0.7 may not be enrolled.

VLU subjects that will use compression during the study should have an ABI that meets the requirements stated in the IFU for the selected compression device.
7. Assign the subject a study number and allocate the subject to either the ALNB (experimental) or SC (comparator group) according to the randomization schedule provided by SealedEnvelope.

8. Photograph the ulcer. Ensure that the calibration ruler with subject's initials and visit date is visible in the image. If the ulcer is debrided, take a photograph of the ulcer immediately prior to and following debridement. Record any debridement and the method of debridement in the electronic Case Report Form (eCRF).
9. Apply dressing according to randomization:
  - For subjects allocated to the ALNB group, apply ALNB as instructed in Section 6.2.2.
  - For subjects allocated to SC, apply a suitable dressing per dressing IFU.
10. Record details of all dressings used for all subjects, (e.g. brand, size, etc.) as well as any treatment applied underneath the dressing, such as Durafiber or Intrasite gel.
11. Assess the ease of applying the dressing (Section 9.5.7), including remains in place and repositioning (if applicable).
12. Instruct the subject to carefully follow the ulcer care instructions until the next dressing change and provide information concerning arrangements for future study visits.
13. Record the total time that the subject spent at the visit (start to finish of ulcer care procedures).
14. If any AE or DevD are observed or reported after application of study product, they must be reported as instructed in Section 12 (Adverse Events and Device Deficiencies). In addition to photographing the ulcer (as above), photograph the dressing if reporting a device deficiency.

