## **5.3 SECONDARY**

Secondary objectives of this study are:

- Ulcer progression (including undermining, necrotic tissue type and amount, exudate type and amount, skin color surrounding the wound, granulation tissue, epithelialization, condition of peri-wound, ulcer dimensions and healing status) at three, six, and twelve weeks
- Healthcare resource use related to the reference ulcer (including number and cost of dressings used, consultations and time used by healthcare professionals (HCP), time in hospital, number and cost of additional treatments, procedures, and investigations) over twelve weeks

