### 9.2.3 Routine Dressing Changes

As ALNB has a maximum recommended wear time of 7 days, routine dressing changes will occur between scheduled Study visits 2, 3, and the End of Study Visit. The number of these visits will vary from subject to subject, based on clinical judgment. These visits will involve subjects

returning to an on-site visit. Dressings should not be given to study subjects; the dressing should only be changed by an HCP at a visit.

1. Question subjects regarding any changes in health or concomitant treatment.
2. Ask the subject to assess the comfort of wearing the dressing since the last visit (see Section 9.5.8).
3. Assess the movement of the dressing (see Section 9.5.9).
4. Remove the old dressing and inspect the ulcer. Complete an ulcer assessment (see Section 9.5.1).
5. Assess the level of pain experienced by the subject when the dressing is removed (see Section 9.5.6).
6. Assess the ease of dressing removal, leakage, and absorption under compression (see section 9.5.10).
7. If any adverse events or device deficiencies are observed or reported, they must be recorded as instructed in Section 12 (Adverse Events and Device Deficiencies).  
NOTE: Photograph the ulcer only if reporting an AE or DevD.
8. Redress the ulcer, if clinically indicated per the subject's randomization assignment:
  - For subjects allocated to the experimental group, apply ALNB as supplied for use in the study, cutting the dressing to size if required and securing with a suitable secondary dressing.
  - For subjects allocated to SC apply a suitable protective dressing, other than ALLEVYN LIFE/ALNB.
9. Record details of all dressings used for all subjects, (e.g. brand, size, etc.) as well as any treatment applied underneath the dressing, such as Durafiber or Intrasite gel.  
For subjects randomized to ALNB, record whether or not the dressing was cut to a smaller size.

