## CONFIDENTIAL DOCUMENT

This document contains confidential information, which is the property of Smith & Nephew, Inc. Do not copy, disclose, or circulate without written authorization from the appropriate Smith & Nephew personnel

The following questionnaire is concerned with the effects that your wound has on your daily life. Please answer the questions carefully by placing a tick in the box which most closely reflects how you feel; it should take about ten minutes to complete.

If you are unsure about how to answer a question, please tick the answer which is closest to how you feel. All answers are confidential.

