5.3 Secondary Endpoints

Ulcer progression variables to be compared between groups at three, six, and twelve weeks including:

- Modified Bates-Jensen Wound Assessment Tool
 - Undermining
 - Necrotic tissue type
 - Necrotic tissue amount
 - Exudate type

CONFIDENTIAL AND PROPRIETARY

This document contains information that is confidential and proprietary to Smith & Nephew PLC and Smith & Nephew, Inc. and is intended for use only by Smith & Nephew and its manufacturer. It shall not be reproduced or copied in whole or in part, nor shall the contents be disclosed by any means without prior written permission from Smith & Nephew, nor shall anyone make any use of it that is contrary to the expressed or implied wishes of Smith & Nephew

Statistical Analysis Plan	
A Pilot Randomized Controlled Trial to Evaluate an Advanced Borderless Dressing (ALLEVYN™ LIFE Non-Bordered) in the Treatment of Chronic Ulcers	Number: CT1603ALF
	ST: 1005
	Version: 1.0, 27-Jul-2018
	Page: 11 of 27

- Exudate amount
- Skin color surrounding the wound
- Granulation tissue
- Epithelialization
- Condition of peri-wound
- Ulcer dimensions
- Ulcer healed status

Healthcare resource use variables (to be compared between groups over the entire twelve week study period) including:

- Dressings used (number and type for both primary and secondary dressings), including use of compression therapy
- Healthcare consultations (number and type)
- Time spent by health care providers (HCP) in treating/caring for reference ulcer
- Time in hospital (nights spent as an inpatient due to reference ulcer)
- Interventions/procedures related to the reference ulcer (number and type), including debridement of the ulcer (curette, scissors, scalpel, forceps, other)
- Concomitant therapies/treatments (number and type) used on the reference ulcer

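### The endpoint is health care provider time on the ulcer, but sites are told to record the subject's elapsed visit time, which ignores staff numbers and includes trial assessments

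*Protocol*

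**What the plan says.** **The endpoint.** SAP 5.3 lists, among the resource-use variables to be compared between groups over twelve weeks, "Time spent by health care providers (HCP) in treating/caring for reference ulcer". The protocol synopsis uses the same definition, and the resource-use objective in Protocol 5.3 includes "consultations and time used by healthcare professionals (HCP".

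**The measurement.** At Visit 1 (Protocol 9.2.2, step 13) the instruction is "Record the total time that the subject spent at the visit (start to finish of ulcer care procedures". The same instruction appears in 9.2.3 (routine changes), 9.2.4 (Visits 2 and 3), 9.2.5 (End of Study Visit) and 9.2.6 (treatment discontinuation). Neither document asks for any other time, for the number of staff present, or for the clock to stop during study procedures.

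**The order of work at a routine change (9.2.3).** Step 4 reads "Remove the old dressing and inspect the ulcer. Complete an ulcer assessment (see Section 9.5.1". Step 5 reads "Assess the level of pain experienced by the subject when the dressing is removed (see Section 9.5.6". Step 6 reads "Assess the ease of dressing removal, leakage, and absorption under compression (see section 9.5.10". Step 7 covers adverse events and device deficiencies. Only step 8 reads "Redress the ulcer, if clinically indicated per the subject's randomization assignment".

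**The concern.** The recorded quantity differs from the named endpoint in two ways.

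- It follows the subject, not the staff. An interval attended by two people counts once.
- It includes work done for the trial. The qualifier in the instruction limits the interval to ulcer care from start to finish, but an interval that starts before the dressing comes off and ends after the new one is on cannot leave out what happens in between.

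The second difference can affect the comparison as well as the level. Routine changes vary in number by clinical judgment (9.2.3), and every site visit due to the reference ulcer is captured as a routine change (9.2.7). An arm with more changes therefore accumulates more assessment time. The pilot is meant to supply health economic data for planning cost-effectiveness work (Protocol 5 and 8.2), and absolute minutes are what such work would cost.

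**Working it through.** The documents state no figure for HCP time, so there is none to reproduce. The check has two parts.

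**1. Where the trial assessments fall**

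| Visit | Removal | Assessments in between | Redressing |
|---|---|---|---|
| Routine change (9.2.3) | step 4 | ulcer assessment (4), pain (5), removal questions (6) | step 8 |
| Visits 2 and 3 (9.2.4) | step 5 | ulcer assessment (5), pain (6), removal questions (7), photographs (8) | step 9 |
| Treatment discontinuation (9.2.6) | step 5 | ulcer assessment (5), pain (6), removal questions (7), photographs (8) | step 10 |
| Visit 1 (9.2.2) | none | assessment is step 5, before randomisation | first application, step 9 |
| End of Study (9.2.5) | step 5 | ulcer assessment (5), pain (6), removal questions (7), photographs (8) | none |

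The assessments are enclosed by removal and redressing in the first three rows. The ulcer assessment in 9.5.1 has eight scored items, with probing for undermining and quadrant-guide estimates, plus peri-wound condition, length, width and depth, healing status and odor.

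Visits 2 and 3 are scheduled once each in both arms, and treatment discontinuation happens at most once per subject. The part that can grow with the number of changes therefore comes from routine changes.

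**2. Size of the effect on the between-arm difference**

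None of these inputs is in the documents, so all are assumptions:

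- m, trial assessment minutes per change: 5, 10 or 15
- c, genuine care minutes per change: 15 or 30
- change interval: 7 days in one arm (either one), and 7, 5, 3.5 or 3 days in the other
- 84 days of treatment for every subject

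Number of changes n = 84 / interval. Excess minutes in the more often changed arm = m × (difference in n).

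| Interval in other arm | n | Extra over 84/7 = 12 | m = 5 | m = 10 | m = 15 |
|---|---|---|---|---|---|
| 7 days | 12 | 0 | 0 | 0 | 0 |
| 5 days | 16.8 | 4.8 | 24 | 48 | 72 |
| 3.5 days | 24 | 12 | 60 | 120 | 180 |
| 3 days | 28 | 16 | 80 | 160 | 240 |

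The sign depends on which arm is changed more often.

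With c and m the same in both arms, the absolute difference is inflated by (c + m)/c:

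- smallest: (30 + 5)/30 = 1.17
- largest: (15 + 15)/15 = 2.0

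The ratio of totals does not move. With 24 against 12 changes it is 24(c + m) / 12(c + m) = 2, the same as 24c / 12c.

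**The case against.** The strongest reply has five parts.

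**The qualifier narrows the interval.** It does, and it may well exclude consent and the CWIS. It cannot exclude steps that lie between removal and redressing.

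**Looking at the ulcer is ordinary care.** This stands in part. The instructions for use tie dressing changes to the condition of the wound and surrounding skin, so inspection belongs in HCP time. What is left as trial work is the formal scoring, the 0 to 10 pain rating, the dressing questions and the photographs. That boundary is a judgment; the documents do not draw it.

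**The case report form may hold more.** It is a separate document and was not available. The claim is therefore limited to what the protocol and SAP tell sites to record.

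**No planned output is affected.** HCP time has no derivation in SAP 7.4 and is missing from the resource-use summaries in Protocol 10.2.2.2 and SAP 7.11. That omission is a separate gap. Closing it with the present field would summarise the wrong quantity.

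**This is a small pilot sized on feasibility.** True, but supplying economic inputs is one of its stated aims.

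Two stronger readings are tempting and are not supported.

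- A reader might infer that the measure favours ALNB because it can be worn for up to seven days. Seven days is a maximum, ALNB changes follow clinical need (6.1.1), no change interval is given for standard care (6.1.2), and both arms attend at least weekly (8.1).
- A reader might add CWIS time to every change, since the form says "it should take about ten minutes to complete". The CWIS is not among the routine-change steps in 9.2.3 and is not ticked for that visit in SAP Table 3.1. At Visits 2 and 3 it comes before dressing removal. At most it affects the level at a few visits.

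**Conclusion.** The mismatch holds. Followed as written, the protocol yields the subject's elapsed time including study procedures, while the synopsis and SAP 5.3 name HCP time on the ulcer. This does not depend on any assumed number.

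The effect on the comparison is conditional. It arises only if the arms differ in number of dressing changes and minutes are compared on the absolute scale. For 12 extra changes the illustration gives 60 to 180 minutes per subject, in either direction. It is zero with equal frequency, and would be smaller where treatment ends early, for example at ulcer closure (7.6). Extra changes also bring real care time, so what is distorted is the size of the absolute difference. The ratio is safe only if care and assessment minutes per change are the same in both arms.

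The undercount of staff is a separate error of unknown size, because the documents do not say how many people attend. The point deserves correction because the remedy is cheap and the variable is meant for economic planning. It does not touch the primary analysis.

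**What to change.** **If collection can still be changed.** In 9.2.2 to 9.2.6, replace the time step with a field for HCP minutes on ulcer care, including inspection that is part of usual care, summed over the staff present. Record time on trial-only scoring, photographs and questionnaires separately. Give sites a short rule on which steps count as care, so that both arms are timed alike. In the SAP, define the 5.3 endpoint as each subject's sum of these care minutes.

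**If data are already collected.** Report the variable by visit type as *visit duration including study procedures*, and do not present it as HCP time.

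**Cost.** One eCRF field definition, one SAP line, and the burden on staff of noting study-procedure time separately. Relabelling after collection costs almost nothing, but it leaves the named endpoint unmeasured.

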### 9.2.3 Routine Dressing Changes

As ALNB has a maximum recommended wear time of 7 days, routine dressing changes will occur between scheduled Study visits 2, 3, and the End of Study Visit. The number of these visits will vary from subject to subject, based on clinical judgment. These visits will involve subjects

returning to an on-site visit. Dressings should not be given to study subjects; the dressing should only be changed by an HCP at a visit.

1. Question subjects regarding any changes in health or concomitant treatment.
2. Ask the subject to assess the comfort of wearing the dressing since the last visit (see Section 9.5.8).
3. Assess the movement of the dressing (see Section 9.5.9).
4. Remove the old dressing and inspect the ulcer. Complete an ulcer assessment (see Section 9.5.1).
5. Assess the level of pain experienced by the subject when the dressing is removed (see Section 9.5.6).
6. Assess the ease of dressing removal, leakage, and absorption under compression (see section 9.5.10).
7. If any adverse events or device deficiencies are observed or reported, they must be recorded as instructed in Section 12 (Adverse Events and Device Deficiencies).  
NOTE: Photograph the ulcer only if reporting an AE or DevD.
8. Redress the ulcer, if clinically indicated per the subject's randomization assignment:
  - For subjects allocated to the experimental group, apply ALNB as supplied for use in the study, cutting the dressing to size if required and securing with a suitable secondary dressing.
  - For subjects allocated to SC apply a suitable protective dressing, other than ALLEVYN LIFE/ALNB.
9. Record details of all dressings used for all subjects, (e.g. brand, size, etc.) as well as any treatment applied underneath the dressing, such as Durafiber or Intrasite gel.  
For subjects randomized to ALNB, record whether or not the dressing was cut to a smaller size.

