#### **9.5 STUDY METHODS AND MEASUREMENTS**

##### **9.5.1 Ulcer Assessments**

###### **Modified Bates-Jensen Wound Assessment Tool**

1. **Undermining:** Assess by inserting a cotton-tipped applicator under the wound edge; advance it as far as it will go without using undue force; raise the tip of the applicator so it may be seen or felt on the surface of the skin; mark the surface with a pen; measure the distance from the mark on the skin to the edge of the wound. Continue process around the wound. Then use a transparent metric measuring guide with concentric circles divided into 4 (25%) pie-shaped quadrants to help determine the percent of wound involved.

2. **Necrotic Tissue Type:** Pick the type of necrotic tissue that is predominant in the wound according to color, consistency, and adherence using this guide

White/gray non-viable tissue	=	May appear prior to wound opening; skin surface is white or gray.
Non-adherent, yellow slough	=	Thin, mucinous substance; scattered throughout wound bed; easily separated from wound tissue.
Loosely adherent, yellow slough	=	Thick, stringy, clumps of debris; attached to wound tissue.
Adherent, soft, black eschar	=	Soggy tissue; strongly attached to tissue in center or base of wound.
Firmly adherent, hard/black eschar	=	Firm, crusty tissue; strongly attached to wound base and edges (like a hard scab).

3. **Necrotic Tissue Amount:** Use a transparent metric measuring guide with concentric circles divided into 4 (25%) pie-shaped quadrants to help determine the percent of wound involved.

4. **Exudate Type:** Before assessing exudate type, gently cleanse wound with normal saline. Pick the exudate type that is predominant in the wound according to color and consistency, using this guide:

Bloody	=	Thin, bright red
Serosanguinous	=	Thin, watery pale red to pink
Serous	=	Thin, watery, clear
Purulent	=	Thin or thick, opaque tan to yellow
Foul purulent	=	Thick, opaque yellow to green with offensive odor

5. **Exudate Amount:** Use a transparent metric measuring guide with concentric circles divided into 4 (25%) pie-shaped quadrants to determine the percent of wound area involved with exudate. Use this guide:

None	=	Wound tissues dry.
Scant	=	Wound tissues moist; no measurable exudate.
Small	=	Wound tissues wet; moisture evenly distributed in wound; drainage involves < 25% dressing.
Moderate	=	Wound tissues saturated; drainage may or may not be evenly distributed in wound;

drainage involves > 25% to < 75% dressing.

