#### **Ulcer length/width/depth**

- Using a ruler, obtain the greatest length and width of the ulcer as well as the deepest depth.

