### 9.5.6 Ulcer Pain Scale

The level of pain associated with removing the dressing from the reference ulcer will be assessed at each study visit. The subject will be asked to rate the level of pain when the dressing is removed on a scale of 0 to 10 (no pain to worst pain). The pain measure will be recorded as a whole number only.

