7.12 Analysis of Exploratory Endpoints

- The average dressing wear time (days) per subject will be calculated and this will be summarized as a continuous variable by treatment group and overall. An estimate of the difference in wear time between treatment groups will be reported with the corresponding 95% confidence interval at twelve weeks only.
- Dressing leakage will be summarized by treatment group and overall
- Ease of dressing application/removal will be summarized by treatment group and overall
- Dressing use (whether dressing was cut and adherence following repositioning) will be summarized by treatment group and overall
- Durafiber/ Intrasite use will be summarised
- Odor control of dressing will be summarized by treatment group and overall
- Absorption of exudate under compression will be summarized by treatment group and overall.
- Reason for dressing change will be summarized by treatment group and overall

CONFIDENTIAL AND PROPRIETARY

This document contains information that is confidential and proprietary to Smith & Nephew PLC and Smith & Nephew, Inc. and is intended for use only by Smith & Nephew and its manufacturer. It shall not be reproduced or copied in whole or in part, nor shall the contents be disclosed by any means without prior written permission from Smith & Nephew, nor shall anyone make any use of it that is contrary to the expressed or implied wishes of Smith & Nephew

Statistical Analysis Plan	 Number: CT1603ALF ST: 1005 Version: 1.0, 27-Jul-2018 Page: 25 of 27
A Pilot Randomized Controlled Trial to Evaluate an Advanced Borderless Dressing (ALLEVYN™ LIFE Non-Bordered) in the Treatment of Chronic Ulcers	

- Pain on dressing removal will be summarized by treatment group and overall and an estimate of the difference between treatment groups will be reported with the corresponding 95% confidence interval.
- Comfort during wear will be summarized by treatment group and overall

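### The removal-pain rating is listed after the full ulcer assessment in all four visit lists that contain it, and Section 9.5.6 does not fix when it is asked

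*Protocol*

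**What the plan says.** **Order of steps.** At a routine dressing change (Protocol 9.2.3), step 4 reads "Remove the old dressing and inspect the ulcer. Complete an ulcer assessment (see Section 9.5.1" and step 5 reads "Assess the level of pain experienced by the subject when the dressing is removed (see Section 9.5.6". Visits 2 and 3 (9.2.4), the End of Study Visit (9.2.5) and Treatment Discontinuation (9.2.6) give the same pair of instructions as steps 5 and 6.

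**Content of the assessment.** Under Protocol 9.5.1, undermining is examined as follows: "Assess by inserting a cotton-tipped applicator under the wound edge; advance it as far as it will go without using undue force". This is repeated around the wound. For exudate the text says "Before assessing exudate type, gently cleanse wound with normal saline". For dimensions it says "Using a ruler, obtain the greatest length and width of the ulcer as well as the deepest depth".

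**The pain scale.** Protocol 9.5.6 states: "The level of pain associated with removing the dressing from the reference ulcer will be assessed at each study visit". The score is a whole number from 0 to 10 and refers to removal. The section does not say whether the question comes before or after the ulcer assessment.

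**Use of the score.** SAP 7.12 states: "Pain on dressing removal will be summarized by treatment group and overall and an estimate of the difference between treatment groups", to be reported with a 95% confidence interval. Protocol 10.2.3 plans the same for three, six and twelve weeks. Among the exploratory endpoints, only wear time also has a planned between-group estimate with an interval.

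**Schedule.** SAP Table 3.1 ticks the pain scale for routine dressing changes but not for treatment discontinuation, whereas 9.2.6 step 6 asks for it there.

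**The concern.** The score is meant to capture one event, the removal of the dressing. If staff work through the list as printed, the subject is asked after the wound has been cleansed, probed around its margin and measured for depth. The rating is then a short-term recollection, and discomfort from the handling in between can influence it.

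If staff instead take the wording about removal as an instruction to ask at that moment, the rating is free of this influence. Both practices fit the text, so sites, or staff within a site, may differ. The protocol allows up to six centers and stratifies randomization by ulcer type only. SAP 7.12 names no model for the pain difference that would account for center.

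At stake is the precision of one exploratory comparison. It still matters somewhat, because Protocol 8.2 wants the pilot to supply an effect-size estimate for a possible full-scale trial, and avoidable measurement noise would carry into that planning.

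**Working it through.** The documents contain no SD, effect size or power figure for the pain score, so there is no stated figure to reproduce. The check has two parts: the order of the steps, which is textual, and an illustration of size, which rests on assumptions.

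**1. Order of steps**

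| Protocol section | Removal and ulcer assessment | Pain rating |
|---|---|---|
| 9.2.3 Routine dressing change | step 4 | step 5 |
| 9.2.4 Visits 2 and 3 | step 5 | step 6 |
| 9.2.5 End of Study | step 5 | step 6 |
| 9.2.6 Treatment Discontinuation | step 5 | step 6 |

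In four of four lists the rating directly follows the assessment. In none does it stand between removal and assessment. In 9.2.4, 9.2.5 and 9.2.6, debridement and photography are listed after the rating, so they are not part of this problem. In the same three lists the CWIS is step 2, ahead of dressing removal, so the primary outcome is not exposed to this ordering.

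**2. Illustrative size**

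Inputs from the documents: 25 ALNB and 15 SC subjects (Protocol synopsis) and a two-sided 95% interval (Protocol 10, SAP 7.1).

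Assumptions: removal-pain SD 2 points; handling carry-over independent of removal pain, with SD 0.5, 1 or 1.5; one rating per subject at a given visit; all 40 subjects contributing.

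Formulas:
- Total SD = √(2² + c²), where c is the carry-over SD
- SE of the difference = total SD × √(1/25 + 1/15) = total SD × 0.3266
- Half-width = t(38) × SE, with t(38) = 2.024

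| Carry-over SD | Total SD | SE | 95% CI half-width | Relative to none |
|---|---|---|---|---|
| 0 | 2.000 | 0.653 | 1.32 | 1.00 |
| 0.5 | √4.25 = 2.062 | 0.673 | 1.36 | 1.03 |
| 1 | √5 = 2.236 | 0.730 | 1.48 | 1.12 |
| 1.5 | √6.25 = 2.500 | 0.817 | 1.65 | 1.25 |

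The relative widening is √(4 + c²)/2 and does not depend on the sample size. The absolute half-widths would be larger if fewer than 40 subjects had a dressing removed at a given visit.

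**The case against.** The strongest reply is that the lists are not declared to be a binding sequence. In 9.2.5 the subject is exited at step 9, yet visit time and adverse events are recorded at steps 10 and 11, so print order is not always time order. Both the visit step and 9.5.6 tie the rating to removal, the recall is within a single visit, and the documents hold no evidence of carry-over. This stands to the extent that contamination is a risk and not an established fact. It does not settle the timing, because the phrase about removal says what is rated and not when the question is put.

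Reach is also limited. The endpoint is exploratory, in a pilot that Protocol 5.6 itself expects is unlikely to show significant differences. The protocol notes that a full ulcer assessment is unnecessary for subjects already discharged or withdrawn from treatment. These points stand and keep the matter small.

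A reader might infer more than the text supports:

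- **That handling pain raises scores in both arms and so hides a dressing difference.** A shift common to both arms cancels in the between-arm difference. Masking would need something like a ceiling effect, and nothing in the documents shows one. Only the added variance remains.
- **That the assessment is the most painful part of the visit.** The documents do not say so. The cleanse is to be gentle, and the applicator instruction is "advance it as far as it will go without using undue force".
- **That a Visit 1 removal-pain score should be added as a covariate.** Such a score would rate whatever dressing the subject arrived in, which is not a baseline of the same quantity, and some subjects may arrive without one. Randomization makes the comparison valid without it.

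**Conclusion.** The point holds as a weakness in measurement timing. All four lists place the rating after cleansing, probing and depth measurement, and 9.5.6 does nothing to protect it. The expected consequence is added noise, from carry-over in the recalled rating and from mixed practice between sites.

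On the assumed SDs, carry-over alone would make the 95% CI about 3% to 25% wider: the half-width goes from 1.32 points to between 1.36 and 1.65. None of those SDs comes from the documents. The noise from mixed practice between sites is not quantified.

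Because the trial is open label, a reader might suspect bias in favor of one dressing. The step order does not support that, since the same assessment is prescribed in both arms. The primary CWIS-PSDL analysis is untouched. The reason to act is that the correction is almost free, not that the damage is large.

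**What to change.** 1. In Protocol 9.5.6, state that the 0-10 rating is taken immediately after the dressing is removed and before any cleansing, probing or measuring.
2. In 9.2.3, 9.2.4, 9.2.5 and 9.2.6, split the combined step so that the order is removal, pain rating, ulcer assessment.
3. Reconcile 9.2.6 step 6 with SAP Table 3.1, so that both agree on whether the rating is collected at Treatment Discontinuation.

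No procedure, visit or eCRF field is added. The cost is the text change itself, handled through the amendment route in Protocol 15 if the study has started.
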